2 RATIONALE

- The routinely used and internationally recognised diagnostic test for assessing the requirement of ambulatory oxygen, Max_6MWT may not correspond to the degree of exercise that patients actually perform when they would use their prescribed ambulatory oxygen (i.e. normal walking speed).
- It is possible that a significant proportion of patients prescribed ambulatory oxygen cannot physiologically benefit from using it as they do not experience a decline in oxygen levels during their normal physical exercise.
- Prescribing of ambulatory oxygen to patients that cannot benefit from it carries additional burdens for the patient, and costs for the NHS, without improving the patient's quality of life.
- If this study shows that a normal walking speed test is a more appropriate assessment for ambulatory oxygen, a higher proportion of patients prescribed ambulatory oxygen will benefit from the therapy and reduce incorrect prescribing of ambulatory oxygen.
- Max_6MWT is a maximal exercise test for most patients with notable respiratory disease and is not always well tolerated (e.g. becoming very breathless). Furthermore, it carries a small but not insignificant risk of acute heart issues and falls. A 6 minute or shorter test at normal walking speed would be safer and easier for a patient to perform.
- Patients' wellbeing could be harmed by misdiagnosing exercise-induced hypoxaemia. Anecdotal evidence suggests some patients become less active after being prescribed ambulatory oxygen for a variety of reasons, including feeling self-conscious or struggling to carry the oxygen cylinder.
- Furthermore, patients may be worried about exercising without ambulatory oxygen if prescribed this therapy due to the perception of risk due to exercise-induced hypoxaemia and potentially incorrect requirement for supplemental oxygen.
- Patients who demonstrate exercise-induced hypoxaemia during a Max_6MWT are required to repeat the Max_6MWT at least once in order to identify the required flow rate of ambulatory oxygen. Titrating the flow of ambulatory oxygen is required to ensure it is sufficient to prevent the exercise-induced hypoxaemia but not too high that could induce hypoventilation and subsequent CO₂ retention. It is plausible that prescribing a flow rate shown to prevent hypoxaemia during a Max_6MWT could far exceed that required to prevent

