4 RESEARCH QUESTION/AIM(S)

To compare the nadir in oxygen saturation reached whilst performing a standard Max_6MWT compared with a Nor_6MWT.

To compare the average oxygen saturation and average drop in oxygen saturation from baseline to the nadir whilst performing a standard Max_6MWT compared with a Nor_6MWT.

To measure when the nadir in oxygen saturation occurs during a Nor_6MWT.

To assess in patients prescribed ambulatory oxygen, what benefit in their symptoms do they report and how does this compare to their Max_6MWT and Nor_6MWT results.

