Only the results of the clinical standard Max_6MWT will be relayed back to the referring member of the clinical care team – they will not see the outcome of the Nor_6MWT. A copy of the IPAQ Elderly Short questionnaire will be provided to fill out during the appointment – this forms the baseline assessment. If they decide to prescribe ambulatory oxygen, questionnaires will be provided to complete either in physical form, or over the phone with a member of the research team. These patients will be identified from the hospital digital patient record. These will include two identical copies of the IPAQ Elderly Short questionnaire – one before they begin ambulatory oxygen and one to complete after four weeks of using ambulatory oxygen – and an Ambulatory Oxygen Questionnaire four weeks after starting ambulatory oxygen. These will provide a surrogate for clinical benefit achieved by the use of ambulatory oxygen. The questionnaires will contain patient identifiable information to enable linking of the data to their test results and, therefore, will be stored securely on a NHS shared drive within HHFT. A secure nhs.net email will be used to receive the completed questionnaires if physical copies are not returned. These data, as a metric of clinical improvement, can then be compared with the outcomes of both the Max_6MWT and Nor_6MWT to determine if these tests can predict patients that will benefit from ambulatory oxygen.

The data from these tests will be stored on the clinical software used in routine testing (SentrySuite, Vyaire) and this may be exported to numerical handling software such as Excel (Microsoft) and stored internally on an NHS shared drive. Follow up will be limited to questionnaire data for those prescribed ambulatory oxygen and this will be arranged either by the physiology team or by the consultants prescribing ambulatory oxygen.

In the event a patient be randomised to the Nor_6MWT and declines to proceed to the Max_6MWT, the results from the Nor_6MWT will be passed on to the medical team and the patient will be withdrawn from the study.

5.1 6-minute walk test protocol

Steps for carrying out the walk test are outlined below:

Group 1: Maximal speed walking test (Max_6MWT) followed by normal speed walking test (Nor_6MWT).

Step 1: Wait at least 10 minutes in a seated position from any previous breathing tests. Baseline blood pressure, heart rate and oxygen saturation obtained. Borg score completed.

Step 2: Instructions provided: "

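### The two four-week questionnaires are timed from different events (using oxygen versus starting it), and no rule covers patients who stop or never start, so the IPAQ change may be selected towards those who persist.

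*Combined protocol and SAP*

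**What the plan says.** The fourth aim in section 4 is "To assess in patients prescribed ambulatory oxygen, what benefit in their symptoms do they report", and how this compares with the results of the two walk tests. Section 4.1 lists the questionnaire results among the other objectives, below the primary and secondary ones.

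Section 5 sets out the collection:

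- At the visit: "A copy of the IPAQ Elderly Short questionnaire will be provided to fill out during the appointment". This is the baseline.
- After a prescription: "If they decide to prescribe ambulatory oxygen, questionnaires will be provided to complete either in physical form, or over the phone".
- Two further IPAQ copies are planned, one before oxygen begins and "one to complete after four weeks of using ambulatory oxygen".
- The third form is "an Ambulatory Oxygen Questionnaire four weeks after starting ambulatory oxygen".
- On scope: "Follow up will be limited to questionnaire data for those prescribed ambulatory oxygen".

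Section 5 treats these questionnaires together as the surrogate for clinical benefit. It then uses them to ask whether either walk test predicts who benefits. Appendix 2 repeats that questionnaires are collected if oxygen is prescribed. The removal rule in section 7.3 concerns patients who cannot complete both walk tests. Nothing in the document says what happens to the four-week forms when a patient stops oxygen or never starts it.

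**The concern.** Eligibility for the questionnaires is set by prescription, but their timing is set by two later events, and those events are not the same. A due date that depends on continued use can make completion of the form depend on how well the treatment went. Patients who give up oxygen early are plausibly less likely to have gained from it. If their follow-up IPAQ is missing, the average change describes persisters rather than everyone prescribed.

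Two things are at stake. First, the reported change in activity could look better than it is for the prescribed group. Second, testing whether a walk test predicts benefit needs patients who did not benefit as well as those who did, and thinning out the former reduces that contrast. This is a further selection within the prescribed group, distinct from the decision to follow up only those prescribed.

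**Working it through.** The plan gives no figure to reproduce. The check is of wording, followed by an illustration of size.

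**Step 1: which form falls due for whom, on the literal wording of section 5**

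| Patient prescribed oxygen | Follow-up IPAQ (four weeks of *using*) | Ambulatory Oxygen Questionnaire (four weeks after *starting*) |
|---|---|---|
| Starts and continues | Due | Due |
| Starts, stops in week 2 | Not reached | Due |
| Never starts | Not reached | Not reached |

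All three rows fall within the section 4 aim, but only the first has a due date for both forms.

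**Step 2: can the other form stand in?** The IPAQ is planned before and after oxygen, so it gives a change score. The Ambulatory Oxygen Questionnaire is planned once, at four weeks. It still informs on patients who stop, but cannot supply a change from baseline. All participants are given an IPAQ at the appointment, so a baseline is available even for patients who never start. What lacks a time point is the follow-up.

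**Step 3: how many patients might be involved (assumed shares).** The planned sample is 82 (section 7.2.1). The documents do not give the share prescribed or the share who stop or never start. Assume 20% to 50% and 10% to 50% respectively.

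- Prescribed: 82 × 0.20 ≈ 16, up to 82 × 0.50 = 41.
- Follow-up IPAQs, lowest: 16 × (1 − 0.50) = 8.
- Follow-up IPAQs, highest: 41 × (1 − 0.10) ≈ 37.

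**Step 4: possible overstatement (assumed values).** Let *s* be the share with no follow-up IPAQ and *g* the amount by which their mean change is worse than that of persisters. The mean for all prescribed is the persister mean minus *s* × *g*, so the persister-only mean overstates it by *s* × *g*.

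| *s* | *g* = 0.25 SD | *g* = 0.5 SD | *g* = 1.0 SD |
|---|---|---|---|
| 0.10 | 0.025 | 0.05 | 0.10 |
| 0.30 | 0.075 | 0.15 | 0.30 |
| 0.50 | 0.125 | 0.25 | 0.50 |

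The same formula applies to a benefit rate. With an assumed 60% benefiting among persisters and 10% among the rest, the overstatement is *s* × (0.60 − 0.10). For *s* = 0.10, 0.30 and 0.40 the true rates are 55%, 45% and 40% against an observed 60%, a gap of 5, 15 and 20 percentage points.

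Both illustrations take the literal reading and assume that no patient who stops or never starts returns a follow-up IPAQ. Neither measures bias in the comparison with the walk tests, which the documents give no basis to quantify.

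**The case against.** The strongest reply is that no exclusion is written. Forms go to everyone prescribed, and section 5 and Appendix 2 both define follow-up by prescription. The two time points stand in one sentence, so *using* may be loose wording for four weeks after starting. This stands in part: a reader might infer that patients who stop are excluded by rule, and the documents do not say so. But adjacent clauses use different words, and section 5 lets either the physiology team or the prescribing consultants arrange follow-up, so the wording could be applied in two ways. Even on the loose reading, a patient who never starts has no due date.

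Second, the surrogate is both questionnaires together, and the Ambulatory Oxygen Questionnaire still reaches patients who start and then stop. That stands, and limits the concern to the IPAQ change for those patients.

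Third, the rationale should not be over-read. Section 2 reports, as anecdote, that "some patients become less active after being prescribed ambulatory oxygen for a variety of reasons". It says less active, not that they stop. Some may go on using oxygen, be due the follow-up IPAQ and show the decline there.

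Fourth, section 5 describes the surrogate as benefit from using oxygen, so a result among users has some relevance. It does, but the section 4 aim concerns patients prescribed oxygen, and a users-only result would need to be labelled as such.

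Finally, the Ambulatory Oxygen Questionnaire and the separate Schedule of Events mentioned in Appendix 2 are not reproduced. Either may already record use or settle the timing.

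**Conclusion.** The concern holds in a limited form. The two four-week forms have different anchors, and nothing in the protocol covers patients who stop or never start. Taken literally, this can select the only before-and-after measure of benefit towards persisters. The direction, towards overstating benefit, rests on the assumption that those who stop or never start fare worse. Across the assumed ranges the overstatement runs from 0.025 to 0.50 SD, but the actual size is unknown because no prescription, stopping or return rates are given.

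Two stronger conclusions are tempting and not supported. One is that the reported benefit comes mainly from those who persisted, which cannot be shown without those rates. The other is that the data cannot reveal prescribing without benefit. Persisters who do not benefit would still be observed, and section 4.2 rests its over-prescribing argument on the SpO₂ difference between the tests, not on questionnaires.

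Only an other objective is affected. The primary and secondary SpO₂ comparisons are untouched. This is a worthwhile low-cost improvement, not a threat to the main result.

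**What to change.** In section 5:

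1. Set both follow-up questionnaires at one calendar point, four weeks after oxygen is supplied, or four weeks after the prescription date if it is never started.
2. Collect both from every participant prescribed oxygen, whether or not it is still being used.
3. At the same contact, record whether oxygen is still used, the date it was stopped or that it was never started, and the reason.
4. Include all prescribed patients in the comparison with the walk tests, with stopping or never starting shown separately.

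This changes data collection and reporting only. The cost is a sentence or two in section 5 and a few questions added to a contact already planned. The small downside is that some usage items will not apply to patients who are not using oxygen. If the Schedule of Events or the Ambulatory Oxygen Questionnaire already covers any of this, section 5 need only be brought into line with it.

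### Uncontrolled questionnaire data from prescribed patients are read as benefit caused by ambulatory oxygen, and the reference IPAQ for any change is left unclear

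*Combined protocol and SAP*

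**What the plan says.** The fourth aim (section 4) is "To assess in patients prescribed ambulatory oxygen, what benefit in their symptoms do they report", and how this compares with the two walk-test results. Section 4.1 places the questionnaire results last under Other objectives, below the primary and secondary lists.

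The detail is in section 5:

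- **Visit.** "A copy of the IPAQ Elderly Short questionnaire will be provided to fill out during the appointment – this forms the baseline assessment". Both walks take place at the same appointment. Section 7.1.2 excludes anyone already prescribed ambulatory oxygen, so this copy is completed off ambulatory oxygen.
- **After a prescription, IPAQ.** Two more copies are issued, "one before they begin ambulatory oxygen and one to complete after four weeks of using ambulatory oxygen".
- **After a prescription, other form.** A different instrument is given once, with no earlier value: "an Ambulatory Oxygen Questionnaire four weeks after starting ambulatory oxygen".
- **Who is followed.** "Follow up will be limited to questionnaire data for those prescribed ambulatory oxygen".
- **What the prescriber sees.** "Only the results of the clinical standard Max_6MWT will be relayed back to the referring member of the clinical care team".
- **Interpretation.** "These will provide a surrogate for clinical benefit achieved by the use of ambulatory oxygen". The results are then set against both walk tests "to determine if these tests can predict patients that will benefit from ambulatory oxygen".

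Section 5 names paired tests for the walk measures. It gives no analysis for the questionnaires, no definition of a change score and no interval between the visit and the start of oxygen.

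**The concern.** To say that oxygen achieved a benefit is a causal statement. The design offers only the course of treated patients over time, so natural recovery, other care started after the visit and expectation are all credited to oxygen. The four-week Ambulatory Oxygen Questionnaire has no earlier value and no comparator, so it cannot separate these either.

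The prediction claim has a further weakness if change is measured from the visit IPAQ. That copy and both walks share one day. A patient in a poor spell may report less activity, desaturate more on the walk and, because the prescriber sees the Max_6MWT, be more likely to receive oxygen. As the spell passes, activity rises without any oxygen effect, and it tends to rise most in those who desaturated most. A walk test that only marks a bad day could then be reported as identifying patients who benefit. Section 4.2 stresses prescribing only to patients who will benefit, so such a report would bear on the question the study is meant to inform.

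**Working it through.** **1. Which copy is the reference?** Two readings of section 5 are open.

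- Visit copy: it is the one called the baseline.
- Pre-start copy: it is listed with the four-week copy in the set of questionnaires that the surrogate sentence follows.

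No sentence computes a change from either, so the text does not settle the matter.

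**2. Is there a planned figure to reproduce?** No. The only design figure, 82 patients in section 7.2.1, concerns the walk comparison, and this point does not depend on it.

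**3. How much could the choice matter?** The documents give no IPAQ variance and no prescribing rate, so every input here is an assumption:

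- oxygen effect zero; 30 of 82 patients prescribed;
- IPAQ variance 1, made up of stable 0.60, transient state 0.25 and error 0.15;
- state low by m = 0.2 to 0.3 SD at the visit, with correlation ρ between successive questionnaires (ρ² from visit to four weeks);
- 25% of the variance of the SpO₂ drop is the visit-day state.

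The tests are also assumed, since none is planned: a paired t-test of change (upper 2.5% tail) and a two-sided 5% test of the correlation between change and drop.

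*Visit copy to four weeks*

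- Mean change = m(1 − ρ²)
- SD of change = √[2 × 0.25 × (1 − ρ²) + 2 × 0.15]
- Correlation with drop = √0.25 × √0.25 × (1 − ρ²) / SD

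*Pre-start copy to four weeks*

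- Mean change = m(ρ − ρ²)
- SD of change = √[2 × 0.25 × (1 − ρ) + 2 × 0.15]
- Correlation with drop = √0.25 × √0.25 × (ρ − ρ²) / SD

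Worked case, visit copy, ρ = 0, m = 0.3: change 0.30; SD √0.80 = 0.894; noncentrality 0.30/0.894 × √30 = 1.84, giving 43% false improvement. Correlation 0.25/0.894 = 0.28, giving 33% false prediction.

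Worked case, visit copy, ρ = 0.5, m = 0.2: change 0.15; SD √0.675 = 0.822; 16% false improvement. Correlation 0.1875/0.822 = 0.23; 23% false prediction.

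Simulation with 20,000 trials per setting agrees with these formulas:

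| Reference copy, ρ | Apparent gain (SD) | False improvement (nominal 2.5%) | False prediction (nominal 5%) |
|---|---|---|---|
| Visit, 0 to 0.5 | 0.15–0.30 | 16–43% | 23–33% |
| Visit, 0.7 | 0.10–0.15 | 11–19% | 15% |
| Visit, 0.9 | 0.04–0.06 | 5–7% | 7% |
| Pre-start, 0 to 0.5 | 0.00–0.075 | 2.5–8% | 5–7% |

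If the drop shares only 5% of its variance with the visit-day state, false prediction from the visit copy is 8–10% for ρ from 0 to 0.5.

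**4. Does the pre-start copy solve it?** Only in part. A second model, also with no oxygen effect, selected the 30% to 50% of patients with the largest drop, let the transient share be 20% or 50%, and made the four-week state independent of the earlier ones. The spurious gain from the visit copy was 0.13–0.46 SD. From the pre-start copy it was zero if the spell had passed before oxygen started, 0.06–0.23 SD if the visit and pre-start states correlated 0.5, and 0.11–0.42 SD at 0.9. A spell that ends only after oxygen starts is still counted as benefit.

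**The case against.** The strongest reply is that the plan already holds the better comparison. The surrogate sentence directly follows the pre-start and four-week IPAQs, so on a natural reading those are the before-and-after pair, and the error rates on that pair are close to nominal in the first model. This stands as far as it goes. A reader might infer that the plan commits itself to change from the visit copy and ignores the pre-start one. The documents do not support that; they leave the reference open.

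A reader might also take 16–43% and 23–33% as the plan's own error rates. They are not. The plan states no change score and no test for the questionnaires, the inputs are chosen, and the rates nearly vanish at high persistence or with little shared variance. The documents do not give the IPAQ's recall period, so how far it captures the state on the day is unknown.

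Finally, the wording is partly hedged (a surrogate, something to be determined), and the item is exploratory. That argues for low severity. It does not rescue the causal phrasing, which is unsupported whichever copy is the reference.

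**Conclusion.** The concern holds in a limited form, as a minor point. Follow-up of prescribed patients alone cannot show benefit achieved by oxygen, nor that a walk test predicts such benefit. This follows from the design and needs no assumed number. Separately, section 5 does not say which off-oxygen IPAQ is the reference. That choice could matter a good deal or very little, depending on how long a poor spell lasts and how strongly it affects the walk. The direction is the same in both models; the size is illustrative only.

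The point reaches the fourth aim and one item under Other objectives. A reader might infer that it weakens the comparison of Max_6MWT with Nor_6MWT. It does not: that comparison is randomised in order, made within patients and independent of the questionnaires.

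**What to change.** Amend section 5 as follows.

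1. Name the pre-start IPAQ as the reference for the four-week change. Beside it, report the visit-to-start change in the same patients, with the date and collection mode of each questionnaire. Label this a descriptive off-oxygen change and not a control, because recovery may be concentrated in that interval and the interval varies. Where the pre-start copy is missing, use the visit copy in a sensitivity analysis.
2. Replace the phrase that attributes clinical benefit to oxygen with *change in reported activity, and patient-reported experience, after starting ambulatory oxygen (uncontrolled)*. Replace the phrase on predicting who will benefit with *are associated with change after starting oxygen*. State that no causal claim of benefit, or of prediction of benefit, will be made from these data.

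The cost is protocol wording and one extra table, with no new questionnaire, visit or patient and no change to care. The downsides are a weaker permitted conclusion, a variable visit-to-start interval and probably some missing pre-start copies.

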SIGNATURE PAGE	ii
LIST OF CONTENTS	iii
KEY STUDY CONTACTS	iv
STUDY SUMMARY	iv
FUNDING	v
ROLE OF SPONSOR AND FUNDER	v
PROTOCOL CONTRIBUTORS	vi
STUDY FLOW CHART	vii
STUDY PROTOCOL	
1. BACKGROUND	1
2. RATIONALE	2
3. THEORETICAL FRAMEWORK	3
4. RESEARCH QUESTION/AIM(S)	4
5. STUDY DESIGN/METHODS	5
6. STUDY SETTING	5
7. SAMPLE AND RECRUITMENT	6
8. ETHICAL AND REGULATORY COMPLIANCE	8
9. DISSEMINATION POLICY	11
10. REFERENCES	11
11. APPENDICES	12

KEY STUDY CONTACTS

Chief Investigator	[name] Lead Respiratory Physiologist Hampshire Hospitals NHS Foundation Trust [name] Email: [contact]
Principle Investigator	[name] Trainee Clinical Scientist Hampshire Hospitals NHS Foundation Trust [name] Email: [contact]
Academic Supervisor (MSc Project for [name])	[name] Professor of Motor Neuroscience Faculty of Science and Engineering [name] Manchester Metropolitan University [name] Email: [contact]
Academic advisor	[name] Faculty Head of Research and Knowledge Exchange, Health and Wellbeing University of Winchester [name] Email: [contact]
Study Co-ordinator	[name]
Sponsor	Hampshire Hospitals NHS Foundation Trust [name]
Funder(s)	Hampshire Hospitals NHS Foundation Trust [name]

STUDY SUMMARY

Study Title	Comparison of the standard Maximal 6-Minute Walk Test against a Normal-speed 6-Minute Walk Test as an alternative and accurate assessment for ambulatory oxygen requirement.
Internal ref. no. (or short title)	Maximal-speed vs Normal-speed 6MWT for ambulatory oxygen assessment.
Study Design	Randomised crossover trial of patients referred for a standard Maximal 6-Minute Walk Test (Max_6MWT) where half of patients will perform the standard Max_6MWT followed by a Normal-speed 6-Minute Walk Test (Nor_6MWT) and the other half a Nor_6MWT followed by Max_6MWT.

Study Participants	Any patient referred for a Max_6MWT with capacity to consent, >18 years of age and able to perform a Max_6MWT.
Planned Size of Sample (if applicable)	82
Follow up duration (if applicable)	N/A
Planned Study Period	18 – 24 months
Research Question/Aim(s)	Does Nor_6MWT provide a better indicator for ambulatory oxygen requirement than the standard Max_6MWT

FUNDING AND SUPPORT IN KIND

FUNDER(S) (Names and contact details of ALL organisations providing funding and/or support in kind for this study)	FINANCIAL AND NON FINANCIAL SUPPORT GIVEN

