11.2 Appendix 2 – Schedule of Procedures

All procedures will be performed in a single visit during a routine outpatient appointment. Collection of questionnaire data will occur after this appointment if subsequently a patient is prescribed ambulatory oxygen either by posting the physical questionnaire to the research team, or by email. In addition, a separate Schedule of Events document has been attached for convenience.

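### Benefit is measured only in patients prescribed oxygen by clinicians who see Max_6MWT but not Nor_6MWT, so the questionnaires cannot show whether Max predicts benefit among all referred patients, nor rank the two tests

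*Combined protocol and SAP*

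**What the plan says.** The relevant text is in section 5 (study design and methods).

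- **What the prescriber sees.** "Only the results of the clinical standard Max_6MWT will be relayed back to the referring member of the clinical care team". The same sentence adds that the Nor_6MWT result is withheld.
- **What everyone completes.** "A copy of the IPAQ Elderly Short questionnaire will be provided to fill out during the appointment – this forms the baseline assessment".
- **What triggers later questionnaires.** "If they decide to prescribe ambulatory oxygen, questionnaires will be provided to complete either in physical form, or over the phone". Prescribed patients complete the IPAQ before starting oxygen and again after four weeks, plus an Ambulatory Oxygen Questionnaire at four weeks.
- **Who is followed.** "Follow up will be limited to questionnaire data for those prescribed ambulatory oxygen". Appendix 2 (section 11.2) repeats the condition: questionnaire data are collected "if subsequently a patient is prescribed ambulatory oxygen".
- **What the data stand for.** "These will provide a surrogate for clinical benefit achieved by the use of ambulatory oxygen".
- **What will be inferred.** They are to be set against both tests "to determine if these tests can predict patients that will benefit from ambulatory oxygen".

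Section 4 words the corresponding aim as one in patients prescribed ambulatory oxygen, and section 4.1 lists the questionnaire results under other objectives. Section 7.1.2 excludes patients already prescribed ambulatory oxygen, so new prescriptions are the only source of benefit data. Section 5 withdraws patients who do Nor first and then decline Max. No definition of benefit, method, sample size or allowance for selection is given for this analysis.

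**The concern.** Benefit is observed in a group selected largely on one of the two tests to be related to it. If most prescriptions follow a positive Max_6MWT, few or no followed patients are Max-negative. The data then say little about whether a positive Max separates patients who benefit from those who do not. On the numerical scale, selection removes the lower part of the Max distribution directly and the lower part of the Nor distribution only through its correlation with Max. Both associations with benefit shrink, by unequal amounts.

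The trial's headline question is "Does Nor_6MWT provide a better indicator for ambulatory oxygen requirement than the standard Max_6MWT". A reader given two correlations with benefit from the same patients will compare them, and a weak Max correlation could be taken as evidence against the standard test when part of the weakness comes from how patients entered the group.

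**Working it through.** The plan has no figure of its own for this analysis. The 82 in section 7.2.1 is for the SpO₂ comparison and is used here only to count patients.

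**Inputs.** From the documents: N = 82, prescribers see Max only, follow-up in prescribed patients only. Assumed, because the documents are silent: joint normality; correlation with benefit 0.40 for each test; Max–Nor correlation ρ of 0.7 or 0.8; the 30% with the largest Max drop are prescribed.

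**Number with an outcome.** 0.30 × 82 = 24.6, about 25.

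**Selection.** For the top 30%, the cut-off is c = 0.524 and the mean above it is λ = φ(c)/0.30 = 1.159. The variance retained is 1 − λ(λ − c) = 0.2645, so the fraction lost is δ = 0.7355. If variable i has correlation sᵢ with the selection variable, its variance becomes 1 − sᵢ²δ, and a covariance cᵢⱼ becomes cᵢⱼ − sᵢsⱼδ. Under a strict cut on Max, s is 1 for Max, ρ for Nor and 0.40 for benefit.

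- Benefit: variance 1 − 0.16 × 0.7355 = 0.8823.
- Max: variance 0.2645; covariance with benefit 0.40 × 0.2645 = 0.1058; correlation 0.1058/√(0.2645 × 0.8823) = **0.22**.
- Nor, ρ = 0.7: variance 1 − 0.49 × 0.7355 = 0.6396; covariance 0.40 − 0.28 × 0.7355 = 0.1941; correlation 0.1941/√(0.6396 × 0.8823) = **0.26**.
- Nor, ρ = 0.8: variance 1 − 0.64 × 0.7355 = 0.5293; covariance 0.40 − 0.32 × 0.7355 = 0.1646; correlation 0.1646/√(0.5293 × 0.8823) = **0.24**.

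Both fall well below 0.40. Nor's lead between equally good tests is 0.02 to 0.04.

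**Lead against sampling error.** In simulated trials of 82 with the 25 largest Max drops followed, the difference between the two observed correlations has an SD of 0.19 to 0.21. Nor is ahead in 55% to 57% of trials, against 50% with no bias.

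**Other prescribing rates**, same formula, true correlations 0.40:

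| Prescribed | Max | Nor (ρ 0.8 to 0.7) |
|---|---|---|
| 20% | 0.20 | 0.23 to 0.25 |
| 50% | 0.25 | 0.27 to 0.28 |
| 70% | 0.29 | 0.30 to 0.31 |

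**Looser selection.** Suppose prescribing follows a propensity that correlates only 0.7 with Max (s = 0.7 for Max, 0.7ρ for Nor, 0.28 for benefit), with 30% prescribed. Max gives 0.33 and Nor 0.33 to 0.34, so the lead is 0.01 or less. Some shrinkage remains.

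**Unequal tests.** With true correlations of 0.50 (Max) and 0.40 (Nor) and 20% prescribed under a strict cut, the observed values are 0.26 and 0.18 if ρ = 0.7, but 0.26 and 0.25 if ρ = 0.5. The same true gap of 0.10 appears as 0.08 or 0.01, depending on a correlation the plan does not know in advance.

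**Precision.** The smallest correlation detectable with 80% power at two-sided 0.05 is tanh[(1.960 + 0.842)/√(n − 3)], with n = 82 × the prescribed fraction. For 10%, 20%, 30%, 50% and 70% prescribed (about 8, 16, 25, 41 and 57 patients) it is 0.84, 0.64, 0.54, 0.43 and 0.36.

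**The case against.** The case for leaving the text alone has real substance.

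- **The plan does not promise a contest.** It asks whether the tests can predict benefit, in patients already stated to be those prescribed (sections 4 and 4.1). It names no sensitivity, specificity or test-against-test contrast. This stands: a reader might infer a planned head-to-head, but none is written.
- **No strict cut-off is documented.** Section 1 says the fall in oxygen level on Max helps inform the decision, and section 5 leaves prescribing to the clinician. A reader might infer that Max must show 100% sensitivity and 0% specificity in the followed group. That would need every prescription to follow a positive Max, which the documents do not say.
- **The outcome is missing for a good reason.** Benefit from oxygen can be seen only in people who receive it. Sending questionnaires to unprescribed patients would not cure the selection; it would only supply a comparison of change without oxygen.
- **The headline question does not rest on the questionnaires alone.** Section 4.2 draws its inference about oxygen requirement from the size of the SpO₂ drop, which is the primary objective. It is wrong to treat the questionnaires as the only route to the research question.
- **The spurious lead for Nor is small**, as the working shows, and with unequal tests the true order can survive.

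These points limit the concern but do not remove it. Stating that the analysis is in prescribed patients does not tell the reader that Max's association is attenuated there by the way patients were selected, and the sentence on prediction carries no such limit.

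**Conclusion.** The point holds as a limit on inference. The questionnaires can describe who reports benefit among patients prescribed oxygen with the Max result in view. They cannot show whether Max predicts benefit among all referred patients, and they cannot support a ranking of Max against Nor.

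In the illustration a true 0.40 is expected to appear as about 0.22 for Max and 0.24 to 0.26 for Nor, from about 25 patients. These values rest on an assumed prescribing rate, assumed correlations, normality and a strict cut on Max; looser selection gives less shrinkage. The main losses are attenuation and imprecision. The stronger reading, that the design will make Nor appear the better test, is not supported: the expected lead is about a tenth to a fifth of its sampling SD (0.02/0.19 to 0.04/0.21).

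This is an other objective and the primary SpO₂ comparison is untouched. The wording should still be corrected before analysis, because the change is cheap and the present sentence invites a conclusion the data cannot carry.

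**What to change.** In section 5, replace the clause on predicting who will benefit with an exploratory analysis restricted to prescribed patients:

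- Estimate the association of the Nor_6MWT SpO₂ drop, kept continuous, with the four-week change in IPAQ and with the Ambulatory Oxygen Questionnaire. A continuous drop avoids having to choose a desaturation threshold, which the protocol does not give.
- Adjust for baseline IPAQ and, where numbers allow, for the Max drop. The two drops are likely to be correlated and the group may be small, so the second adjustment should be conditional on the number prescribed.
- Report confidence intervals and the number of patients prescribed.
- State that the results apply only to patients prescribed oxygen on the basis of Max_6MWT, that the before/after change has no untreated comparison, and that the questionnaires will not be used to rank Max against Nor or to claim that either is the better indicator.

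The cost is analysis wording only: no new visits, patients or questionnaires. The downside is a narrower claim.
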